1.3.2. Safety Endpoints

- Incidence rate and severity of treatment-emergent adverse events (TEAEs)
- Incidence rate and severity of study drug-related TEAEs
- Vital signs, electrocardiogram (ECG), and clinical laboratory test results

1.3.3. Other Endpoints

- PK: Measurement of plasma concentrations of KPL-716
- Immunogenicity: Measurement of anti-drug (anti-KPL-716) antibodies (ADA)

1.4. Estimands

The primary estimands defined for main endpoints are summarized below in [Table 1](#). More details are provided in [Section 4.6](#).

Table 1: Summary of primary estimands for main endpoints

Endpoint Category	Estimands			Analysis set-level summary
	Endpoint(s) ^a	Analysis set	Intercurrent event(s) strategy and missing data handling	
Primary objective: To evaluate the efficacy of subcutaneous (SC) KPL-716 vs. placebo in reducing pruritus in prurigo nodularis (PN) subjects experiencing severe pruritus				
Primary endpoint	Percent change from baseline in weekly average Worst Itch– Numeric Rating Scale (WI-NRS) at Week 16	mITT	
The intercurrent events will be handled as follows:
 
 Discontinuation of study treatment before Week 16: Off-study treatment data up to Week 16 will be included in the analysis (treatment policy strategy). Taking rescue/prohibited medications that impact efficacy analyses prior to Week 16: data will be set to missing values after the medication usage, and the participant's worst postbaseline observation before the time of the medication usage will be carried forward (WOCF) to impute missing endpoint value (hypothetical strategy) 
In addition, the missing data imputation rules are as follows:
 
 Missing data at Week 16 will be imputed with Multiple Imputation (MI) method. 	Analysis of Covariance (ANCOVA) model will be used with treatment and randomization factors of sex and years since the first nodule observed (i.e., ≥ 10 vs. <10 years) as fixed effect factors, baseline as covariate.

Endpoint Category	Estimands			Analysis set-level summary
	Endpoint(s) ^a	Analysis set	Intercurrent event(s) strategy and missing data handling	
Key secondary endpoint	Proportion of subjects achieving at least a 4-point reduction from baseline in weekly average WI-NRS at Week 16	mITT	
The intercurrent events will be handled as follows:
 
 Discontinuation of study treatment before Week 16: Off-study treatment data up to Week 16 will be included in the analysis (treatment policy strategy). Taking rescue/prohibited medications that impact efficacy analyses prior to Week 16: Participants will be considered as non-responders (composite strategy). 
In addition, the missing data imputation rules are as follows:
 
 Having missing data at Week 16: Participants will be defined as non-responders. 	CMH test adjusted by randomization stratification variables: sex and years since the first nodule observed (i.e., ≥ 10 years vs. < 10 years) will be used.

Endpoint Category	Estimands			Analysis set-level summary
	Endpoint(s) ^a	Analysis set	Intercurrent event(s) strategy and missing data handling	
Secondary objective: To evaluate the effect of SC KPL-716 vs. placebo in reducing disease severity in PN subjects experiencing severe pruritus				
Key secondary endpoint	Proportion of subjects achieving clear (0) or almost clear (1) from baseline in PN-IGA at Week 16	mITT	
The intercurrent events will be handled as follows:
 
 Discontinuation of study treatment before Week 16: Off-study treatment data up to Week 16 will be included in the analysis (treatment policy strategy). Taking rescue/prohibited medications that impact efficacy analyses prior to Week 16 assessment: Participants will be considered as non-responders (composite strategy). 
In addition, the missing data imputation rules are as follows:
 
 Having missing data at Week 16 assessment: Participants will be defined as non-responders. 	CMH test adjusted by randomization stratification variables: sex and years since the first nodule observed (i.e., ≥ 10 years vs. < 10 years) will be used.

^a Additional secondary objectives/endpoints are not included in this table but will be handled with a similar strategy as the endpoint type (i.e., continuous, proportion) at other weeks, otherwise specified.

1.5. Determination of Sample Size

The Phase 2b sample size calculation is based on the primary efficacy endpoint (percentage change from baseline of WI-NRS at Week 16) using a two-sample t-test.

Approximately 180 subjects in total will be equally randomized to the 4 arms of Phase 2b. At Week 16, 53% and 30% reduction in weekly average of WI-NRS are assumed for KPL-716 and placebo arms, respectively. For each comparison, assuming treatment effect of 23% difference in weekly average WI-NRS reduction from baseline at Week 16 and standard deviation of 35%, and two-sided alpha of 0.05, 38 subjects in each arm will provide 80% power to detect the treatment effect. Approximately 45 subjects in each arm will be randomized assuming 15% drop out during the 16 weeks of treatment.

The sample size calculation was performed using nQuery version 8.5.

2. STUDY ANALYSIS SETS

The following analysis sets will be defined for Phase 2b.

2.1. Randomized Subjects

Randomized subjects will include all subjects with randomization number assigned.

2.2. Modified Intent-to-Treat (mITT) Analysis Set

All randomized subjects who receive at least one dose of KPL-716 or placebo and have at least 1 daily WI-NRS score in the double blind Treatment Period will be included in the modified intent-to-treat (mITT) analysis set. All mITT analyses will be based on each subject's randomized treatment assignment.

2.3. Safety Analysis Set

All randomized subjects who received at least one dose of KPL-716 or placebo will be included in the safety analysis set. Safety analyses will be based on the treatment that was administered to each subject.

2.4. Per Protocol (PP) Analysis Set

The PP analysis set includes all mITT subjects who have no important protocol deviations that may potentially bias efficacy analyses of the study. These deviations will be pre-specified prior to study unblinding/database lock.

2.5. OLE Analysis Set

OLE analysis set includes all randomized subjects who consented to OLE period and received at least one dose of KPL-716 for OLE period.

2.6. PK Analysis Set

The PK analysis set includes any subjects who received KPL-716 and who had at least one PK sample.

3. GENERAL CONSIDERATIONS

All analyses and summaries will be produced using SAS® version 9.4 (or higher).

For inferential statistical analyses, each arm of KPL-716 (Arm A KPL-716: 540 mg Q4W, Arm B KPL-716: 360 mg Q4W, Arm C KPL-716: 120 mg Q4W) will be compared to placebo. Unless otherwise specified, all tests will be at two-tailed using pre-specified level of significance 0.05.

Descriptive statistics (n, mean, standard deviation [SD], median, Q1, Q3, minimum, and maximum) will be presented for continuous variables. For continuous efficacy endpoints, least square (LS) mean, LS mean difference, standard error (SE), and 95% confidence interval (CI) will be calculated.

For categorical variables (including binary variables), counts and percentages will be presented. For binary efficacy endpoints, 95% CI for difference in proportion and p-values will be presented.

Subject listings in all randomized subjects, will be provided for all efficacy and safety data. In general, the subject listings will be sorted by treatment group, subject number and assessment date (and time, if applicable).

3.1. Baseline Value and Change from Baseline

The baseline value of efficacy parameters except is defined as the last non-missing value before randomization and prior to the first dose of study medication otherwise specified.

For daily collected efficacy endpoints (WI-NRS), baseline is calculated as weekly average of non-missing scores from 7 days prior to randomization (Day -7 to Day -1).

For safety endpoints, baseline is defined as the last non-missing value obtained prior to the first dose in DB Period otherwise specified.

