1.2. Study Design

This is a randomized, double-blind, placebo-controlled study to investigate the efficacy, safety, tolerability, PK, and immunogenicity of KPL-716 administered SC in subjects with moderate to severe PN experiencing severe pruritus.

[figure not shown]
The Phase 2b study ([Figure 1](#)) consists of a 4-week screening period and a 16-week double-blind (DB) period, followed by a 36-week open-label-extension (OLE) period. Approximately 180

subjects with moderate to severe PN experiencing severe pruritus will be randomized (at 1:1:1:1 ratio) into one of the following 4 arms:

- Arm A: KPL-716, 540 mg, SC, every 4 weeks (Q4W)
- Arm B: KPL-716, 360 mg, SC, Q4W
- Arm C: KPL-716, 120 mg, SC, Q4W
- Arm D: Placebo, SC, Q4W

A total of 4 doses of study drug will be administered during the DB Period to measure the efficacy, safety, and PK of KPL-716.

Figure 1 Phase 2b Study Design Diagram

After the DB period, all subjects will have the option to receive KPL-716 360 mg SC, Q2W during the OLE period to evaluate the long-term safety and PK of KPL-716. For subjects who complete the DB period but choose not to participate in OLE, or who terminate earlier, an End of Study (EOS) visit will be required 4 weeks following the date of last study drug dose.

Subjects will follow the schedule below:

- Screening period (minimum 7 days and maximum 28 days)
- DB period (Day 1 [Baseline] to Week 16)
- OLE period (End of Week 16 to Week 52)

The allowable visit window from Week 2 to Week 16 is \pm 2 days and thereafter to Week 52 is \pm 3 days.

Randomization and Dosing:

Subjects will be randomized 1:1:1:1 into one of the following 4 arms: KPL-716 540 mg SC, Q4W; KPL-716 360 mg SC, Q4W; KPL-716 120 mg SC, Q4W; or placebo SC, Q4W. At the end of DB period, all subjects will have the option to enter the OLE period to receive KPL-716

360 mg SC Q2W. Stratification will be performed based on sex and years since first nodule observed (i.e., ≥ 10 years vs. < 10 years).

Efficacy Assessments:

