3.2. Study Day and Treatment Day

For efficacy endpoints analyses, study day is defined as the number of days from randomization date to the event/visit date. It is calculated as follows:

- If the event date falls on or after randomization date,

Study day = Event or visit date – randomization date + 1

- If the event date falls before randomization date,

Study day = Event or visit date – randomization date

For safety endpoints analyses, treatment day is defined as the number of days from DB first dose date to the event/visit date. It is calculated as follows:

- If the event date falls on or after DB first dose date,
Treatment day = Event or visit date –DB first dose date + 1
- If the event date falls before DB first dose date,
Treatment day = Event or visit date –DB first dose date

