3.3. Analysis Visits and Study Period

For efficacy analyses, DB period is defined from randomization up to the first OLE dose if subjects enter OLE treatment period, or end of study in subjects not enrolled in OLE period, unless specified. OLE period is defined from OLE first dose up to the end of study. If assessment time is available, assessments should be further differentiated by time compared to OLE first dose. If assessments are collected on the same day as OLE first dose date and no assessment times are available, those assessments should be counted into DB period.

For safety analyses, DB period is defined from first dose up to the first OLE dose if subjects enter OLE treatment period, or end of study if subjects not enrolled in OLE period.

Efficacy assessments

For the efficacy assessment, the reference date for the derivation of relative days of events or findings will be the randomization day. If a subject receives treatment dose prior to the randomization by mistake, the reference date of efficacy assessment will be the date of the first treatment dose administration for that subject.

For the daily WI-NRS, weekly average will be aligned by study periods. For DB period, weekly average will be calculated based on every 7 days increment starting on Day 1. For week 16, only assessments before the first dose of OLE period will be included for weekly average calculation. Time windows are specified in [Table 2](#) below.

Table 2: Time window of weekly average WI-NRS in DB period

Analysis week	Time windows referring to randomization date
Baseline	-7 to -1
Week 1	1 - 7
Week 2	8 - 14
Week 3	15 - 21
Week 4	22 - 28
Week 5	29 - 35
Week 6	36 - 42
Week 7	43 - 49
Week 8	50 - 56

Week 9	57 - 63
Week 10	64 - 70
Week 11	71 - 77
Week 12	78 - 84
Week 13	85 - 91
Week 14	92 - 98
Week 15	99 - 105
Week 16	106 - min(113, Day of OLE first dose)

The time window of weekly average NRS in OLE period will start from the day after the first dose of OLE period as specified in [Table 3](#).

Table 3: Time window of weekly average WI-NRS in OLE period

Analysis week	Time windows referring to OLE first dose date
Week 17 - OLE	2 - 8
Week 18 - OLE	9 - 15
Week 19 - OLE	16 - 22
Week 20 - OLE	23 - 29
Week 21 - OLE	29 - 36
Week 22 - OLE	37 - 43
Week 23 - OLE	44 - 50
Week 24 - OLE	51 - 57
Week 25 - OLE	58 - 64
Week 26 - OLE	65 - 71
Week 27 - OLE	72 - 78
Week 28 - OLE	79 - 85
Week 29 - OLE	86 - 92
Week 30 - OLE	93 - 99
Week 31 - OLE	100 - 106
Week 32 - OLE	107 - 113

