		Physical examination, Vital signs, Body weight, Clinical lab blood tests	ECG Pregnancy test	Urinalysis
Baseline*	1	ADA	≤ 1	≤ 1
Week 2	15		2 - 22	
Week 4	29		23 - 43	

Week 8	57	44 - 71	2 - 85
Week 12	85	72 - 99	
Week 16	113	100 - OLE first dose	86 - OLE first dose 2 - OLE first dose

* up to first dose date/time

The visit mapping in OLE period will start from the day after the first dose of OLE period using the time window specified in [Table 7](#).

Table 7: Time window for safety variables in OLE period

Visit	date	Time windows		
		Physical examination, Vital signs, Body weight, Clinical lab blood tests	ECG	Urinalysis, Pregnancy test
Target Day referring to OLE first dose	ADA			
Week 18 - OLE	15	2 - 22		
Week 20 - OLE	29	23 - 71		
Week 32 - OLE	113	72 - 169		2 - 169
Week 48 - OLE	225	170 - 239		170 - 239
Week 52 - OLE	253	240 - EOS	2 - EOS	240 - EOS

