4.7.1. Adverse Events

Adverse events will be mapped to PT and SOC using the most up to date MedDRA of the version at database lock. A treatment-emergent AE (TEAE) is defined as any event not present before exposure to study drug or any event already present that worsens in either intensity or frequency after exposure to study drug. Furthermore, if an AE cannot be determined as treatment-emergent due to incomplete/missing date, conservatively, it will be considered as treatment emergent and included in the summary tables. For subjects who enter OLE, TEAEs which occur (based on AE start dates) before OLE first dose date will be summarized into DB period, otherwise into OLE period. If AE occurring time is available, time should be compared to OLE first dose date and time for AE period derivation.

The following TEAE summaries will be summarized as an overview.

- Any TEAEs
- Drug-related TEAEs
- TEAE by maximum severity (mild, moderate, severe)
- Serious TEAEs (SAEs)
- Drug related serious TEAEs
- TEAEs leading to dose interruption
- TEAEs leading to treatment discontinuation
- TEAEs leading to study discontinuation
- Death
- TEAE of special interest

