4.7.2. Clinical Laboratory Tests

Blood and urine samples will be collected for clinical laboratory evaluations (including clinical chemistry, hematology, urinalysis, and serology) at the time points specified in Protocol

Appendix 1. The data collected in different units were converted to SI units (the International System of Units) for summary.

The following summaries by study periods will be provided by laboratory category of chemistry, hematology, and urinalysis.

- Numeric laboratory values will be summarized as descriptive statistics for both actual value and change from baseline (post baseline minus baseline) by week. If lab values are recorded as <xx, the limits of xx will be used for summary.
- Shift table summarizing subject incidence of laboratory normal range (Low, Normal, High) at baseline contrasted with lowest or highest post baseline. Parameters with bidirectional abnormality (low and high) will be presented by post baseline lowest and highest.

All laboratory data will be listed.

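### The single pre-double-blind safety baseline mixes placebo-period change into the open-label safety results of placebo subjects who switch to KPL-716

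*SAP*

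**What the plan says.** SAP 1.2 offers open-label treatment to every arm, placebo included: "all subjects will have the option to receive KPL-716 360 mg SC, Q2W during the OLE period to evaluate the long-term safety and PK of" the active drug. For a subject in Arm D, the first OLE dose is the first dose of KPL-716 in this phase.

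For safety, SAP 3.1 states: "For safety endpoints, baseline is defined as the last non-missing value obtained prior to the first dose in DB Period otherwise specified". The closing words leave room for exceptions, but SAP 3.3 and SAP 4.7 contain none for the OLE. SAP 3.2 uses the same anchor for timing: "For safety endpoints analyses, treatment day is defined as the number of days from DB first dose date to the event/visit date".

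Other safety rules do recognise the switch. SAP 3.3 closes the double-blind period at it ("For safety analyses, DB period is defined from first dose up to the first OLE dose if subjects enter OLE treatment period") and, with its Table 7, resets the visit windows ("The visit mapping in OLE period will start from the day after the first dose of OLE period using the time window specified in").

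SAP 4.7 summarizes laboratory, vital-sign and ECG data by treatment, visit and study period. The laboratory outputs in SAP 4.7.2, produced per period, include: "Shift table summarizing subject incidence of laboratory normal range (Low, Normal, High) at baseline contrasted with lowest or highest post baseline". SAP 4.7.4 adds ECG shifts by period and the incidence of a QTcF rise above 60 msec from baseline.

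For adverse events, SAP 4.7.1 counts as treatment-emergent both new events and "any event already present that worsens in either intensity or frequency after exposure to study drug". It then assigns the period: "For subjects who enter OLE, TEAEs which occur (based on AE start dates) before OLE first dose date will be summarized into DB period", and to the OLE otherwise, using clock time where available.

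**The concern.** The OLE is there to characterise the longer-term safety of KPL-716. Placebo-origin subjects are the only group observed on study without KPL-716 immediately before they start it, so change from just before the switch is the natural readout of first exposure. The plan resets the clock for OLE visits at the switch but leaves the reference value 16 weeks earlier.

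A laboratory abnormality that arose on placebo and persisted would then appear as a shift in the KPL-716 period. An abnormality present at entry, resolved on placebo and back on KPL-716 would not appear as a new shift.

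The adverse-event rule has a smaller gap of the same kind. The definition of treatment-emergent includes worsening, but the period depends only on when the event began.

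**Working it through.** **How many subjects.** The plan's own figures (SAP 1.5) are a difference of 23 points, SD 35, two-sided alpha 0.05 and 80% power. The two-sample t-test gives 37.3, rounded up to 38 per arm. With 15% dropout, 38 / 0.85 = 44.7, so 45 per arm, and 4 × 45 = 180. Both stated figures reproduce.

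- Ceiling for placebo-origin subjects: 180 / 4 = 45 (25%).
- After 15% dropout: 45 × 0.85 = 38.25, about 38.
- Share of the OLE with equal entry across arms: 38.25 / (38.25 + 114.75) = 25%.
- Share with unequal entry (assumed, as the documents give no rate): 70% placebo and 90% active gives 31.5 / (31.5 + 121.5) = 21%; 90% and 70% gives 40.5 / (40.5 + 94.5) = 30%.

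**What the OLE change measures.** For a placebo-origin subject, let d be the change from the double-blind baseline to the last value before the first OLE dose, and e the change from that value to the OLE visit. The plan reports d + e; only e follows KPL-716.

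- A placebo-origin column is displaced by the mean of d.
- A pooled OLE column, if one is made, is displaced by about 0.25 × d. Assumed d of 0.1, 0.2 and 0.5 SD gives 0.025, 0.05 and 0.125 SD.
- The QTcF flag tests d + e > 60 msec. It can fire when e is 60 or less, and can miss e > 60 when d is negative.

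**What happens to shifts** (placebo-origin subject, N = normal, H = high):

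| Day 1 | Week 16 pre-dose | OLE highest | Shift under SAP 3.1 | Shift from pre-OLE value |
|---|---|---|---|---|
| N | H | H | N to H | H to H |
| H | N | H | H to H | N to H |
| N | N | H | N to H | N to H |

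The first two rows are classified differently. The documents give no rate for either pattern, so no corrected count can be computed.

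**Adverse events.** An event starting after the first OLE dose goes to the OLE, as it should. An event that starts before that dose and worsens after it depends on data entry:

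- If the worsening is a new record with its own start date, it goes to the OLE.
- If it stays on the first record, it remains in the double-blind period. The maximum-severity summary in SAP 4.7.1 then takes in the later grade, and the OLE table omits the event.

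Protocol 7.5.1.1 asks for onset, duration and severity, and treats worsening of a pre-existing condition as an adverse event. It does not say how to record an on-study event that later worsens. For scale only, if 2% to 10% of placebo subjects had such an event (assumed), the count runs from 38 × 0.02 = 0.8 to 45 × 0.10 = 4.5, about 1 to 5 subjects. The rule applies equally to the three KPL-716 arms.

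**The case against.** One pre-study baseline keeps both periods on a single scale, and the information is not lost. SAP 4.7.2 to 4.7.4 also summarize actual values, Week 16 has its own window in Table 6, and SAP 3 provides listings of all safety data. OLE safety is descriptive and the randomized comparison of laboratory, vital-sign and ECG data is untouched. All of this stands, and it limits the weight of the point. It does not supply the missing summary: means by visit do not yield within-subject shifts or QTcF exceedances since the switch. Showing the OLE by randomized arm would separate the placebo-origin subjects without removing d. The SAP commits to that display only for efficacy (SAP 4.6).

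Three stronger readings are tempting and are not supported.

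- *The adverse-event rule ignores the switch.* It does not. SAP 4.7.1 cuts at the first OLE dose, by time where available. The gap covers only events that straddle that dose, worsen and stay on one record, and the documents do not settle how such events are recorded.
- *The drug-placebo difference is understated.* An event that began on placebo is rightly a double-blind placebo event, so its incidence there does not change. Later severity could be carried back in all four arms. Protocol 4.5 also predicts higher concentrations in the OLE than on the blinded Q4W doses, so KPL-716 arms could be affected too. The net direction is unknown.
- *Forty-five subjects will start KPL-716 at Week 16.* That is a ceiling, because OLE entry is optional and 15% dropout is assumed.

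**Conclusion.** The baseline point holds on the text. SAP 3.1 sets one safety baseline, nothing overrides it for the OLE, and OLE change and shift results for placebo-origin subjects therefore contain their placebo-period change. It concerns at most about 45 subjects, about 38 after assumed dropout, and fewer if some decline. The displacement equals d in a placebo-origin column and about a quarter of d in a pooled one at equal entry. The size of d is not given, so material distortion is possible but not shown. Double-blind laboratory, vital-sign and ECG comparisons are unaffected.

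The adverse-event point is secondary. It is confined to straddling events that worsen and depends on a recording convention that the documents leave open. Both are inexpensive improvements to a descriptive safety readout.

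**What to change.** **SAP 3.1.** For subjects randomized to placebo who enter the OLE, add an OLE safety baseline: the last non-missing value before the first OLE dose. Use it for that group's OLE change, shift and QTcF >60 msec summaries. Show them in a separate placebo-to-KPL-716 column and do not mix them into a pooled one. Keep the existing baseline for all double-blind summaries and for subjects randomized to KPL-716.

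**SAP 4.7.1.** Where severity changes are dated, count an event that starts before and worsens after the first OLE dose as an OLE TEAE at its worsened grade, in every arm. Report its double-blind severity as the level reached before that dose. State how worsening is recorded on the adverse-event form.

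**Cost.** A few sentences and some programming. No new assessments are needed, because Protocol Appendix 1 places blood samples and ECG before dosing on dosing days. Vital signs are taken both before and after dosing, so the pre-dose reading must be selected. Protocol 8.7 leaves safety analysis details to the SAP. The downside is two baseline definitions in the OLE tables, which need a footnote. The adverse-event part cannot be applied where severity changes carry no date.
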